We hypothesize this rehabilitation strategy will also be successful in human subjects. The proposed project aims to translate animal hemianopia research to a noninvasive rehabilitation system for use by human visual hemianopia patients. The specific objectives of the program can be enumerated as follows:

Specific Aim 1: Determine the efficacy of an intervention using cross-modal stimulation training to restore visual function in homonymous hemianopia patients.

Specific Aim 2: Assess the long-term effects of rehabilitation through follow-up visits after the completion of rehabilitation.

Methods and Measures

Design

This study will test a rehabilitation technique for treating visual hemianopia and compare results against measures from patients pre-intervention. We will recruit all interested patients with visual hemianopia and will assess visual field, visual capabilities, quality of life, and brain images as part of our research measures.

Setting

Rehabilitation training sessions and progress tests will be performed on the Wake Forest Baptist Medical Center Campus and in subjects' homes. Since administering the Humphrey visual field test requires specific equipment, subjects will visit an optometrist's office for these tests. Subjects will perform the remaining visual tests on the Wake Forest Baptist Medical Center Campus.

Subjects selection criteria

- **Inclusion Criteria**
 - Adult volunteers diagnosed with homonymous visual hemianopia / hemianopsia (ages 18-99)
 - MRI or CT scan demonstrating lesion in the occipital lobe of the brain and/or affecting white matter tracts that provide visual input to the occipital lobe of the brain
 - Brain injury due to ischemic or hemorrhagic causes that occurs after age 18 and at least 6 months prior to screening visit
 - Demonstration of good fixation on visual training task
- **Exclusion Criteria**
 - Volunteers who are unable to complete the study tasks or understand instructions
 - Subjects that are not able to provide written consent or verbal assent
 - Subjects who are not available to complete all rehabilitation sessions
 - Physical, neurological or mental disability that would interfere with study intervention
 - Concurrent participation in "vision therapy" other than standard occupational or physical therapy

- **Sample Size**

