The goal of this project is to obtain proof the rehabilitation technique has the potential to be successfully translated to humans. To achieve this goal, we will recruit a sample size of 10 hemianopia subjects in this study in hopes of having at least 5 participants complete all study sessions. This study is exploratory; the findings from this study will be used to design future studies. The observed treatment response pattern will be reported, and those data used for informed estimates of incidence for future research. Prior animal model studies demonstrated a high success rate in the rehabilitation strategy, with 100% of 11 hemianopic cats regaining visual field. Assuming that 80% of subjects will have a successful result, using n=5 subjects will allow for estimation of a 95% confidence interval with width 0.35 units either side of the estimate [22].

Interventions and Interactions

Interventions

Cross-Modal Visual Auditory Rehabilitation - Cross-modal visual auditory rehabilitation is based on the rehabilitation paradigm derived from previous animal model studies. The rehabilitation will be carried out using a virtual reality rehabilitation (VR) system. The rehabilitation system uses a customized commercial wireless VR headset, the Samsung Gear VR, to run custom-made rehabilitation software.

The cross-modal rehabilitation software provides a gray colored, neutral environment for patients, with minimal distractions from rehabilitation. Subjects will be asked to fixate on a colored fixation spot in the center of the visual field for 1 second before being randomly presented with either a visual stimulus in the normal intact visual field or a spatiotemporally coincident audio-visual stimulus in the hemianopic side. Auditory-visual stimulus and visual stimulus will be presented at a ratio of 9:1 respectively. The design of the fixed, predictable timing and 9:1 ratio will help subjects shift their attention to the blind field.

[figure not shown]

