Peripheral Visual Field Test - Since the Humphrey visual field test only measures up to 30° in the periphery, an additional peripheral visual field test will be administered using a semi-circular frame device (fig. 1) set 50 cm in front of the subject with LED lights acting as visual stimulus, located at azimuths of 15°, 30°, 45°, 60°, and 75°, as well as a center fixation light. Lights will be presented at a random time with a fixation period between each trial and locations selected randomly. Subjects will be asked to fixate on the center fixation light while lights are presented at random locations at random times (0-1.5 seconds). Upon detecting a light, subjects will press a button. Subject responses will be used to determine how far in the periphery, up to 75°, a subject can see. The test will present a total of 5 trials at each location in both the intact and hemianopic side, as well as 5 trials with no stimuli.

This test uses the free-field frame device to position visual and auditory stimuli, in the form of LED lights and speakers, at different angles of the patient. The patient is asked to maintain visual fixation on a lit LED light straight ahead during the test. Speakers will play a brief burst of white noise from a random location 15° or 45° on either the left or right side. The subject will be asked to identify where the sound is originating from either verbally or using a button response pad. During this test, subjects' eyes may be videotaped or photographed. These recordings or photos will be reviewed by a member of the study team to confirm the subject is able to properly maintain visual fixation.

Figure 1: Free-field frame device

track rehabilitation progress. The test consists of 30 trials with visual stimulus presented either 15°, 30°, 45° in either the hemianopia field or the intact field at random time intervals.

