The virtual reality headset and headphones will provide visual and auditory stimulation used in the rehabilitation training. Each rehabilitation session will consist of 200 trials. At the end of each rehabilitation session, subjects will perform a brief 2-minute VR visual field progress test with the VR system to track rehabilitation progress. The rehabilitation will be considered complete once patients can reliably detect stimuli 45° in the hemianopic field.

If patients cannot detect stimuli at 15° by the end of 30 days of rehabilitation, they will repeat the rehabilitation for one more month, in order to determine if the slow progress or lack of progress is caused by simply not spending enough time performing rehabilitation.

Study Session 63: Post Rehabilitation Tests - Subject visual field did not increase (1 hour)

If no visual field improvement (measured by virtual reality visual field progress tests) has occurred at the end of the 2nd round of rehabilitation, subjects will complete one last visit, where they will be given the

NEI VFQ-25 and VA LV VFQ-48 questionnaires to complete. This visit will occur on the Wake Forest Baptist Medical Center campus.

Study Session 33: Post Rehabilitation Tests - Subject visual field increase (1.5 hours)

If a subject shows visual field expansion in the virtual reality visual field progress test, subjects will be given a **Peripheral Visual Field Test, NEI VFQ-25 and VA LV VFQ-48 Questionnaires** in order to measure visual field expansion and improvements in quality of life.

In previous animal studies, rehabilitated hemianopic animals could only detect spatial frequencies of 2 cycles/degree compared to over 5 cycles/degree in the (normal) intact animals. We hypothesize the subcortical visual pathway mediating the restored visual functions may not have the same capabilities as the visual cortex it is replacing. Therefore, recovered vision may have lower visual acuity. The different pathways involved in cross-modal rehabilitation may also affect abilities for shape recognition in the newly recovered visual field. We will explore whether this is the case with a simple **shape recognition test, visual acuity test, and color vision test** during this visit. Subjects will complete this visit on the Wake Forest Baptist Medical Center campus.

Study Session 34: Humphrey Visual Field Post-Intervention Test (1 hour)

Subjects will report to an optometrist for a **Humphrey Visual Field** perimetry test.

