Study Session 35: 3 Month Post-Intervention Follow-up Tests (1 hour)

Subjects will complete a follow-up visit 3 months after the end of rehabilitation on the Wake Forest Baptist Medical Center campus. The follow-up visit will consist of a peripheral visual field test, and NEI VFQ-25 and VA LV VFQ-48 questionnaires.

Study Session 36: 6 Month Post-Intervention Follow-up Tests (1 hour)

Subjects will complete a final follow-up visit 6 months after the end of rehabilitation on the Wake Forest Baptist Medical Center campus. The follow-up visit will consist of a peripheral visual field test, and NEI VFQ-25 and VA LV VFQ-48 questionnaires.

Outcome Measure(s)

The primary outcomes for all participants will be the visual field measurements from Humphrey Visual Field and peripheral frame test, with comparisons made before (visits 1 and 2) and after treatment (visits 34 and 35 or visits 63 and 64).

Secondary outcome measures will include differences in quality of life questionnaire results from before (visit 1) and after treatment (visit 33 or 63) and changes in VR progress test results during the course of rehabilitation (visits 3-32 and 33-62 if a subject repeats rehabilitation).

Exploratory outcome measures will be collected in subjects with restored visual fields. The qualities of recovered visual field will be examined with visual acuity, color recognition, and shape recognition tests after rehabilitation (visit 33 or 63).

Analytical Plan

Results will be analyzed initially using descriptive statistics. The improvement of visual detections will be assessed by using a two-way ANOVA on the percentages of visual detections to stimuli presented in the hemianopic hemifield in the peripheral visual field tests before and after rehabilitation. Comparisons for subjects will be done using chi square tests for proportions, and t-tests or ANOVA procedures for continuous variables. Other inferential statistical analysis will be conducted as appropriate.

Human Subjects Protection

Subject Recruitment Methods

Protocol version: 2

Protocol updated 7.01.20

Subjects with homonymous hemianopia on either the left and right side of the visual field will be recruited using resources from Wake Forest University Health Sciences' Clinical and Translational Science Institute (CTSI). Members of the PI's research team will perform recruitment. Coordination of potential participants' visit will be done by phone or in person conversation or by email.

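### The Analytical Plan leaves subject out of its before/after two-way ANOVA and does not say that its other tests are paired, although one small group is compared with itself

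*Combined protocol and SAP*

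**What the plan says.** The Design section describes a single group and will "compare results against measures from patients pre-intervention". Sample Size recruits 10 subjects "in hopes of having at least 5 participants complete all study sessions" and calls the study exploratory.

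Under Peripheral Visual Field Test there are five azimuths (15° to 75°), and "The test will present a total of 5 trials at each location in both the intact and hemianopic side". Each test therefore gives five hemianopic-side percentages per subject.

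The Analytical Plan is one paragraph. It starts with descriptive statistics. Improvement on this test is then "assessed by using a two-way ANOVA on the percentages of visual detections to stimuli presented in the hemianopic hemifield", before and after rehabilitation. It continues: "Comparisons for subjects will be done using chi square tests for proportions, and t-tests or ANOVA procedures for continuous variables". Further inference is left open. Nowhere do the documents mention a paired, matched, repeated-measures or mixed analysis, or a subject term.

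On who supplies the data, Outcome Measure(s) states: "The primary outcomes for all participants will be the visual field measurements from Humphrey Visual Field and peripheral frame test". The session descriptions are narrower. Study Session 33 gives the peripheral test "If a subject shows visual field expansion in the virtual reality visual field progress test". Study Session 63 applies "If no visual field improvement (measured by virtual reality visual field progress tests) has occurred at the end of the 2nd round of rehabilitation", and lists only the two questionnaires.

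**The concern.** Every before value has an after value from the same person, and each person contributes five values per test. An ordinary two-way ANOVA treats all of them as independent. Two errors then act in opposite directions. Stable differences between subjects enter the error term and make the test too cautious. Variation that affects a subject's whole session is averaged as if it were independent at each location, which makes the test too ready to declare a change.

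This ANOVA is the only test that the plan ties by name to a primary measure. Two analysts following the text could report different p-values and intervals from the same data. Future studies are to be designed from these results, and that needs the within-subject change and its spread. The number of usable pairs is also unclear, because the documents disagree on who has the post-rehabilitation test.

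**Working it through.** **1. The plan's own figure.** Sample Size gives a 95% CI half-width of 0.35 for 80% success at n=5. 1.96 × √(0.8 × 0.2 / 5) = 0.351. It reproduces and does not depend on this point.

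**2. Degrees of freedom.** Five locations at two times give 10 values per subject, or 50 at n=5. A time-by-location ANOVA has 10 cells, so residual df = 10n − 10 = 10(n − 1) = 40. The within-subject test of time has n − 1 = 4. Critical t is 2.02 against 2.78. With 3 or 4 pairs, df are 20 or 30 against 2 or 3.

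**3. Equivalence.** On one simulated n=5 dataset, repeated-measures ANOVA gave F(1,4) = 0.2174, p = 0.665. A paired t-test on subject means gave t² = 0.2174, p = 0.665. The ordinary ANOVA gave F(1,40) = 0.435, p = 0.513. The first two are the same test; the third is not.

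**4. Type I error, n=5, nominal 5%.** The documents give no SDs, so these are assumptions, not bounds. There were 20,000 simulated trials per setting, with 5 locations × 5 trials before and after, a slope of 0.4 logit per location step, and normal subject and subject-by-session effects on the logit scale. Baseline is mid-field detection of a typical subject. Entries are ordinary time × location / ordinary time × subject (locations as replicates) / paired t, in %.

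| Subject SD / session SD | Baseline 20% | Baseline 5% | Baseline 1% |
|---|---|---|---|
| 2 / 0 | 0.3 / 2.3 / 3.6 | 0.9 / 3.2 / 2.3 | 1.7 / 3.7 / 0.8 |
| 1 / 0.25 | 2.3 / 4.3 / 4.3 | 3.4 / 4.9 / 3.3 | 2.6 / 3.5 / 0.9 |
| 1 / 0.5 | 6.1 / 11.3 / 4.2 | 5.3 / 8.8 / 3.0 | 3.4 / 4.9 / 1.1 |
| 1 / 1 | 16.4 / 30.3 / 3.9 | 13.8 / 24.2 / 2.6 | 7.0 / 12.4 / 1.0 |

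Repeat runs put the time × location range at 0.4% to 17%. A separate normal-theory simulation (residual SD 1) gave 0.2% to 24% without a subject term and 4.6% to 5.3% for the subject-level test.

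**5. Power, n=5, a rise of 1 logit.**

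| Baseline, SDs | Time × location | Paired t |
|---|---|---|
| 20%, 2/0 (mean 30% to 44%) | 26% | 42% |
| 20%, 1/0.5 (mean 26% to 43%) | 59% | 38% |
| 5%, 2/0 | 22% | 20% |
| 5%, 1/0.5 | 43% | 19% |
| 1%, 2/0 | 13% | 4% |
| 1%, 1/0.5 | 19% | 5% |

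In the first row, the time × subject layout has 71%. With 3 or 4 pairs there, paired-t power is 15% or 26%.

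**6. Mixed response.** Sample Size assumes 80% success. Let each subject respond with probability 0.8, by 4 logits (an assumption), at n=5 across the four SD pairs. At baseline 5%, paired t has 58–72% and time × location 95–99%. At baseline 1% the figures are 32–52% and 93–99%. A rerun over both baselines gave 31–74% against 93–99%. By hand: changes of 80, 80, 80, 0, 0 points have mean 48 and SD √(7680/4) = 43.8, so t = 48 / (43.8/√5) = 2.45 on 4 df, p = 0.07.

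**7. Sessions against the outcome definition.** Outcome Measure(s) places the after measurements at visits 34 and 35, or 63 and 64.
- Session 33: peripheral test, only with VR field expansion.
- Session 34: Humphrey test only.
- Session 35: the 3-month follow-up, with a peripheral test.
- Session 36: the 6-month follow-up, with a peripheral test.
- Session 63: questionnaires only, as the last visit of subjects without improvement.
- Session 64: not described.

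As listed, a subject without VR improvement has no after value on the peripheral test.

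**The case against.** The plan never says that its tests are unpaired. The design compares patients with their own earlier measures, and the outcome section speaks of differences and changes, so a within-subject reading is natural. The study is exploratory, its sample size rests on a CI width, and no decision rule uses this p-value. All of that stands and limits the severity.

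The numbers also limit the harm. Ordinary time × location error is 0.3% to 6.1% in nine of the 12 settings in step 4; only a session SD of 1, which no document figure supports, takes it higher. A reader might infer that the ordinary ANOVA generally produces false positives, or generally misses real change. Neither is supported. In step 5 the paired t-test has more power in one setting only (baseline 20%, SDs 2/0). Near the floor it is very conservative and has less power. Averaging over locations also hides how far into the periphery a subject sees, which is what the test is meant to show.

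A reader might also infer that chi-square is planned for before/after proportions. The plan does not say so; the single-arm design only makes it plausible.

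What does not stand is that a natural reading settles the matter. Making subject one of the two factors, with locations as replicates, also fits the text, yet gave up to 30% error. The error term has to be stated.

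**Conclusion.** The point holds as a gap in specification: no subject term, error term or pairing is stated for before/after data from perhaps five people. It does not hold as a claim that the plan prescribes an invalid test.

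If the ANOVA is run in ordinary form, its p-value and interval are unreliable in either direction. Type I error is about 0.4% to 17% for time × location at n=5, with clear inflation only when session-to-session variation is large. These sizes rest wholly on assumed SDs and baselines; the contrast of 40 df with 4 does not.

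The conflict between the session descriptions and Outcome Measure(s) is real but separate. A paired analysis does not remove selection on VR improvement. Severity: minor to should-fix.

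**What to change.** In the Analytical Plan:
- State that the ANOVA factors are time and location, that subject is a repeated (random) factor, and that time is tested against subject-by-time.
- Give the equivalent summary: mean within-subject change in detection percentage over the five hemianopic locations, with a 95% CI on n − 1 df and a plot of each subject. Showing results by location as well keeps the information on peripheral extent.
- Use paired forms for any before/after t-test or proportion.
- Lead with the estimate, CI and individual results, because a 4-df test is imprecise. Do not justify this by the exact-test floor of 2 × 0.5⁵ = 0.0625, which does not apply to a paired t-test.
- Report how many subjects have both tests.

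Reconcile Study Sessions 33 to 36 and 63 with Outcome Measure(s) on who has the post-rehabilitation peripheral test and which visit supplies the after score.

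Cost: the analysis change is wording only and needs no new data. Nominal power at n=5 is materially lower in many settings, especially near a floor baseline or when some subjects do not respond (step 6), and the interval will be wide, more so with 3 or 4 pairs. If the reconciliation settles on all participants, subjects without improvement need one more test.

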Grating Acuity Test - Visual acuity will be tested using a standard grating test. Subjects will be presented with a 10°x10° square window filled with either a horizontal or vertical grating, located 5° from the fixation point on a computer screen in their hemianopic or intact side. Gratings will start from 0.2 cycles per degree and progress to larger sizes of 0.5, 1.0, 1.5, 2.0, 2.5, 3.0, 4.0, then 5.0 cycles per degree. The test will comprise of 5 trials for each grating. Subjects will be asked to identify whether the grating is horizontal or vertical by either pushing buttons on a response pad or verbally. Responses will be recorded for each question.

Virtual Reality (Visual Field) Progress Test - At the end of each rehabilitation session, subjects will perform a brief 5-minute test using the VR system to

Color Vision Test - The color vision test will be administered on a computer. While focused on a central fixation point, subjects will be presented with a colored $10^\circ \times 10^\circ$ block located 5° in the anopic hemifield and be asked to verbally identify the color. A member of the research team will record these responses. The color in each trial will be randomly picked among the color choices of white, black, red, orange, yellow, green, blue, and violet. Each color will be displayed at least 3 times.

Shape Recognition Test - Subjects will be presented with basic shapes in their hemianopic side on a computer monitor. Shapes will be colored black and be displayed on a white background in a $10^\circ \times 10^\circ$ square window located 5° in the previously hemianopic side. Subjects will be asked to fixate on a central point and verbally identify each object or express uncertainty. Verbal responses will be recorded for later analysis. During this test, subject responses may be audiotaped in order to capture their responses. This test will consist of 20 trials.

Questionnaires

The NEI VFQ-25 and VA LV VFQ-48 questionnaires are designed to assess the taker's quality of life regarding limitations due to low vision.

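### No intact-side comparison is prespecified, although training is meant to shift attention to the blind side and intact-side detection is measured

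*Combined protocol and SAP*

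**What the plan says.** **Intended mechanism.** The intervention section sets the stimulus mix: "Auditory-visual stimulus and visual stimulus will be presented at a ratio of 9:1 respectively". Its purpose is explicit: "The design of the fixed, predictable timing and 9:1 ratio will help subjects shift their attention to the blind field". The Background makes the same point.

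**What is measured.** The Peripheral Visual Field Test uses azimuths of 15°, 30°, 45°, 60° and 75°. "The test will present a total of 5 trials at each location in both the intact and hemianopic side", with 5 further trials carrying no stimulus. The VR progress test at the end of each training session has 30 trials at 15°, 30° or 45° in either field; the split by side is not given.

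**What is analysed.** The Analytical Plan opens with descriptive statistics, then specifies a two-way ANOVA whose data are limited as follows: "percentages of visual detections to stimuli presented in the hemianopic hemifield in the peripheral visual field tests before and after rehabilitation". Its factors are not named. Chi-square tests, t-tests or ANOVA, and other inference as appropriate, follow without being attached to a variable. Under Outcome Measure(s), the Humphrey and frame-test fields are primary and change in the VR progress test is secondary; none is limited to one side.

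**Who is tested afterwards.** Session 33 gives the frame test to subjects whose VR progress test shows expansion. Session 63, the last visit for those without improvement, lists only the two questionnaires. Outcome Measure(s) nevertheless cites visits 63 and 64 as after-treatment visits for the primary outcomes in all participants.

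**The concern.** Two things are at stake.

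- **Safety.** The intact field is the one these subjects rely on. If attention moves toward one side, a cost on the other is a reasonable thing to check. The safety section assigns monitoring to the principal investigator but names no intact-field check.
- **Interpretation.** Aim 1 is about restored visual function, and there is no control group. The intact side is the natural within-subject comparison. A blind-side gain with stable intact-side detection fits recovery better than a gain with an intact-side fall. A rise in button presses on both sides and on blank trials points to a change in responding. An analysis confined to the hemianopic side sees none of these distinctions.

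**Working it through.** **1. The plan's own precision figure.** The Sample Size section states: "Assuming that 80% of subjects will have a successful result", n = 5 gives a "95% confidence interval with width 0.35 units either side of the estimate". Check: 1.96 × √(0.8 × 0.2 / 5) = 0.351. It reproduces and is not in dispute; it fixes n = 5 for what follows.

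**2. Exposure.** At 200 trials per session and 9:1, there are 180 blind-side and 20 intact-side stimuli per session. Over 30 full sessions that is 180 × 30 = 5,400 against 20 × 30 = 600. These counts ignore early completion and restarts, and they describe exposure, not harm.

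**3. Intact-side data available.**
- Frame test: 5 azimuths × 5 trials = 25 per test, or 125 per time point with 5 subjects.
- VR progress test: if the 30 trials split evenly by side (assumption), 15 × 30 = 450 per subject over 30 sessions.

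**4. What the ANOVA can see.** Take two subjects with the same blind-side gain G. One stays at 25/25 on the intact side; the other drops to 19/25, a change of −24 percentage points. Both contribute the same values to the ANOVA. The side-by-time contrast (blind-side change minus intact-side change) is G − 0 = G for the first and G − (−24) = G + 24 for the second. The contrast separates them, but an intact-side loss makes it larger. It must therefore be shown with the change on each side, not alone.

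As a guide within one subject, treating trials as independent, Fisher's exact two-sided test gives p = 0.022 for 25/25 v 19/25 and p = 0.050 for 25/25 v 20/25.

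**5. Precision with 5 completers.** The half-width of the 95% CI for mean intact-side change is t × SD/√n, with t = 2.776 on 4 degrees of freedom. The SD of change is assumed, since the documents give none:

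| SD of change (points) | Half-width (points) |
|---|---|
| 5 | 6.2 |
| 10 | 12.4 |
| 15 | 18.6 |

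A simulated paired t-test (two-sided 5%, 25 trials before and after, 95% true detection before, occasion-to-occasion SD of the true rate 0 to 0.10, all assumed) has power of about 6–21% for a fall to 90%, 32–79% for a fall to 80% and 68–98% for a fall to 70%. A non-significant result would say little, so estimation is the better form.

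**6. Chance falls.** For an unchanged subject with true rate p and independent trials, the probability of a lower count at retest is f = (1 − P(tie))/2, where P(tie) is the sum of squared binomial(25, p) probabilities. For five unchanged subjects, the probability of at least one fall is 1 − (1 − f)⁵.

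| p | P(tie) | f | At least one of five |
|---|---|---|---|
| 0.90 | 0.191 | 0.405 | 0.925 |
| 0.95 | 0.273 | 0.364 | 0.896 |
| 0.99 | 0.644 | 0.178 | 0.625 |

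A rule triggered by any fall would thus fire on noise in 18–40% of unchanged subjects, and at least once in a group of five with probability 62–93%.

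**The case against.** A reader might infer that the intact side enters no analysis at all and that a loss there would go unseen. The documents do not support this. The primary and secondary field outcomes are not restricted by side, all results are to be described, the Humphrey field is mapped before and after, and VR progress results reach the study team during training. An intact-side loss could surface in any of these. What stands is narrower: nothing commits the team to report it. No Humphrey index is named either, so a whole-field summary could offset an intact-side loss against a blind-side gain.

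A reader might also infer that training is designed to draw attention away from the intact side, or that it damages that side. The protocol speaks only of attention moving to the blind field, and no passage reports or predicts intact-side loss. It remains a possibility worth checking.

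It is tempting to say that every decision rule looks only at the blind side. Only the completion rule names the hemianopic field; the repeat and routing rules name no side, although the blind side is the natural reading.

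Intact-side detection cannot settle attention versus recovery on its own. It may be near ceiling, so attention could shift without a measurable fall, and a fall could reflect fatigue. This stands, and it is why blank-trial responses and fixation data belong beside it.

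Finally, the study is exploratory and small: a "sample size of 10 hemianopia subjects in this study in hopes of having at least 5 participants complete all study sessions". That argues against another significance test, but not against reporting data already being collected.

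**Conclusion.** The point holds as a gap in prespecification. The training has a stated attention-shifting purpose, 25 intact-side trials are recorded in each frame test, and the one analysis tied to a named variable excludes them. In an uncontrolled study this leaves out both a safety check and a within-subject comparison. It does not show that harm occurs or that a loss would necessarily be missed.

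The gain from closing the gap is modest: with about 5 completers, mean intact-side change is estimated to within about 6 to 19 points, depending on an assumed SD of 5 to 15. The chance-fall figures rest on independent trials and true rates of 90–99%. A post-training frame test is secure only for subjects with VR expansion until the visit descriptions are reconciled. This is an inexpensive improvement worth making, not a flaw that invalidates the study.

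**What to change.** In the Analytical Plan, beside the hemianopic-side result:

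- Report before/after intact-side detection in the frame test (25 trials per test) by subject and location, for all subjects tested at both times.
- Give the mean change on each side and the side-by-time contrast, each with a 95% CI and no significance test.
- Report the response rate on the 5 blank trials, before and after.
- Tabulate intact-side VR progress-test detections by session for the principal investigator's safety review.
- State that blind-side gains will be interpreted together with the intact-side estimate and its CI, the blank-trial responses and any fixation data. Do not adopt a rule that any intact-side fall disqualifies a gain.

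Separately, reconcile the Session 63 description (questionnaires only for subjects without improvement) with Outcome Measure(s) (visits 63 and 64 as after-treatment visits for all participants), so that it is clear who has an after-treatment frame test.

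Cost: a little more analysis, with no new data in subjects tested at both times. Precision will be limited, ceiling effects are possible, and some apparent responders may be described more cautiously.
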